10.3 Accrual

We perform surgery in 60-80 patients per year at Washington University with similar characteristics and estimate approximately 30-40 patients/year may be eligible for and will participate in this trial. We anticipate enrollment of approximately 2-3 patients per month.

10.4 Statistical Analyses

10.4.1 Patient Disposition

The number of patients discontinued, the reasons for discontinuation, and the amount of therapy administered will be summarized by patient and by reason for discontinuation by arm.

10.4.2 Protocol Deviations

All significant deviations will be summarized by patient and by type of deviation.

10.4.3 Demographics and Baseline Characteristics

Subject demographic and clinical characteristics will be summarized to characterize the population. Descriptive summaries will include means, standard deviations, medians, ranges for continuous variables and frequency and percentage for categorical variables. They are presented by total and each arm, respectively.

10.4.4 Endpoint Analysis

The primary endpoint is percent weight loss. Weight (kg) will be collected weekly during radiation within each arm. The percent weight loss from the baseline is calculated at any post-baseline. The generalized estimating equation (GEE) model with identity link function will be used to analyze this percent weight loss data, in which the correlation among the repeated measures from the same patient need be considered. The autoregressive

of first order as working correlation structure will be used. The GEE model includes baseline weight and time points. The p-value is estimated to assess whether the percentages of weight loss across all time points are different. Least square means for percent weight loss at each time point and mean differences between any time points will be estimated, and their standard errors will be calculated within the use of GEE sandwich method when accounting for within-patient correlation.

The secondary endpoints include proportion of PEG tube placements for all enrolled patients, the serum creatinine changes in patients receiving POAmCRT, proportion of the narcotics administration of patients 6 weeks after POAmCRT, and RFS. Proportions of PEG tube placements for all enrolled patients and the narcotics administration of patients 6 weeks after POAmCRT and their associated 95% confidence intervals will be calculated assuming a binomial distribution²³. The serum creatinine is measured at the baseline and six weeks after POAmCRT. The paired t-test will be considered to test the change.

Disease recurrence rate at 24 months post-treatment (DRR-24) in each arm is calculated for each arm. The proportion and 95% CI from binomial distribution will be shown for Arm 1. If 95% upper CI is smaller than 20%, then the risk of disease recurrence is deemed as acceptable. If 95% lower CI is larger than 20%, then the risk of disease recurrence is deemed as unacceptable. Given our small sample size, there are some uncertainties. Therefore, we do not test the hypothesis about (DRR-24) but provide a preliminary data for planning future studies.

PFS will be calculated from the date of surgery to the date of progression, death of any cause, or last known date alive. OS will be calculated from the date of surgery to the date of death or last known date alive. PFS and OS will be evaluated using Kaplan Myer.

The exploratory endpoint includes the measures of Quality of Life (QOL). QOL are measured at baseline/during treatment/one year after completion of treatment on all arms. Similarly, the GEE model will be used to analyze the longitudinal QOL data.

Data on the toxicity in each arm will be collected for each subject, including frequency, type, and severity of adverse events. All analyses were conducted using SAS (SAS Institute, Cary, NC) at the two-sided 5% significance level.

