Low risk patients will be assigned to Arm 2 where they will be treated with de-intensified RT: 42 Gy (vs 60 Gy) and no cisplatin at all. Reduction in treatment-related toxicity is expected in Arm 2.

High risk patients will be assigned to Arm 3 where they will be treated with standard intensive therapy, so reduction in treatment-related toxicity is not expected in this group.

Mucosal damage is the key mediator of most of the acute toxicity for POART and POACRT. The primary endpoint for the **MINT** trial is weight loss, a reliable, easily measured and practical surrogate marker of mucosal toxicity. **Historical data showed that the percent weight loss during POACRT in patients with HPV-related OPSCC was 7.39%. The primary hypothesis of this trial is that the percent weight loss of patients in Arm 1 during POAmCRT will be 3.7% (50% reduction).**

Secondary endpoints of mucosal toxicity to be determined include the proportion of patients who had PEG tubes placed, who experienced a doubling of the serum creatinine from baseline (a surrogate of dehydration and/or cisplatin toxicity), and who remained on narcotics at 6 weeks after POAmCRT. The secondary hypothesis for this trial is the proportion of patients with the composite endpoint of PEG tube placement/doubling of the serum creatinine/requirement for narcotics at 6 weeks after POAmCRT will be reduced from the historical control of 72.6% to 36.3% (50% reduction). Similar endpoints will be monitored for Arm 2, although the number of patients in this arm is expected to be small based on historical data. As such, we will not develop formal hypothesis testing for Arm 2, but will report the toxicity data in descriptive form.

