2.0 STUDY ENDPOINTS AND OBJECTIVES

2.1 Primary Objective

1. To determine the percent weight loss in patients during POAmCRT (Arm 1) starting at Day 1 and ending on the last day of RT.

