10.2 Sample Size Calculation

The primary endpoint is percent weight loss from Day 1 of treatment to last day of RT. The sample size calculation is based on the primary endpoint only. Our historical data showed that the mean and standard deviation of percent weight loss during POACRT in patients with HPV-related OPSCC are 7.39% and 5.46%, respectively. The primary hypothesis of this trial is that the percent weight loss of patients in Arm 1 during POAmCRT will be 3.7% (50% reduction). Twenty patients

will have 80% power to detect the percent weight loss difference if assuming the standard deviation of 5.46% using a two-sided one-group t test at the type I error of 5%. We will enroll 24 patients in Arm 1 accounting for 15% drop-out²². We estimate that 14 patients will be enrolled in Arm 2 and 6 patients will be enrolled in Arm 3 for a total of 40 patients.

In December 2019, we reached the 40 patient enrollment mark. However, Arm 1 had enrolled only 13 of the target of 20 patients at that time. In June 2020, we plan to increase enrollment to reach 7 additional patients on Arm 1, or 20 additional patients onto any arm, whichever comes first.

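### The primary analysis in section 10.4.4 omits the test that sized the trial (Arm 1 weight loss against 7.39%); its only primary p-value compares time points with each other

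*Combined protocol and SAP*

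**What the plan says.** The hypothesis and sizing are specific. Sections 1.9 and 10.2 both put the expected Arm 1 result as a number: "The primary hypothesis of this trial is that the percent weight loss of patients in Arm 1 during POAmCRT will be 3.7" percent, half the historical figure. Section 2.1 fixes population and window: "To determine the percent weight loss in patients during POAmCRT (Arm 1) starting at Day 1 and ending on the last day of RT". Section 10.2 repeats the window ("The primary endpoint is percent weight loss from Day 1 of treatment to last day of RT"), gives the historical mean and standard deviation ("percent weight loss during POACRT in patients with HPV-related OPSCC are 7.39% and 5.46%, respectively"), and describes what a sample of 20 achieves as follows: "will have 80% power to detect the percent weight loss difference if assuming the standard deviation of 5.46% using a two-sided one-group t test". Type I error is set to 5%.

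Section 10.4.4 then describes the analysis of the same endpoint differently. Percent weight loss at each post-baseline weight enters a GEE with identity link, AR(1) working correlation, baseline weight and time point. The p-value is defined as follows: "The p-value is estimated to assess whether the percentages of weight loss across all time points are different". The planned estimates are described so: "Least square means for percent weight loss at each time point and mean differences between any time points will be estimated". The section closes by setting all analyses "at the two-sided 5% significance level". It contains no reference to 7.39%, to a one-sample test, or to a success criterion for weight loss.

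**The concern.** The two sections test different null hypotheses:

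- **Section 10.2:** Arm 1 mean loss at the end of RT equals 7.39%.
- **Section 10.4.4:** mean loss is the same at every weekly time point.

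Neither implies the other. A regimen with exactly the historical loss, accumulating week by week, makes the first null true and the second false. A regimen whose whole loss of 3.7% occurred in the first week and then held steady would meet the trial's target, yet leave the across-time test nothing to detect.

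A team following 10.4.4 as written would therefore report a primary p-value that says nothing about benefit over historical treatment. Because the section applies a 5% level to it, that p-value is likely to be read as the trial's result. If the team instead compares the last estimate with 7.39%, the form of that comparison would be chosen after the data are in hand.

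**Working it through.** **1. Reproduce the sizing (section 10.2).** Inputs: reference mean 7.39, target 3.7, SD 5.46, two-sided alpha 0.05, n = 20.

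- Difference: 7.39 − 3.70 = 3.69 points. Standardised effect: 3.69 / 5.46 = 0.676.
- Noncentrality: 0.676 × √20 = 3.02, on 19 degrees of freedom.
- Power from the noncentral t distribution: 81.8% at n = 20 and 79.6% at n = 19, so 20 is the smallest n reaching 80%.
- Drop-out: 20 / 0.85 = 23.5, rounded up to 24, as stated.

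The sizing is sound, and it belongs to the one-sample t test.

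**2. What that test would require of the data.** With SD 5.46 and n = 20, the 95% CI half-width is 2.093 × 5.46 / √20 = 2.56 points. An observed mean loss below 7.39 − 2.56 = 4.83% would reject 7.39%.

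**3. What the across-time test responds to.** Suppose mean loss rises in equal steps over four weeks. The gap between week 4 and week 1 is then three quarters of the final loss: 0.75 × 7.39 = 5.54 points with no benefit, and 0.75 × 3.7 = 2.78 points at the target. The test has more to detect when the regimen fails.

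**4. Illustration by simulation.** The documents do not give the weekly trajectory or the within-patient covariance, so these are assumed: n = 20, four weekly weights, linear mean, end-of-RT SD 5.46. The model is the GEE of 10.4.4 with categorical time and sandwich covariance; 1,500 replicates per cell. Entries are the percentage of trials in which the across-time test is significant, Wald / score:

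| Assumed covariance | True loss 7.39% (no benefit) | True loss 3.7% (target) |
|---|---|---|
| Random slope, noise SD 1 | 99.9 / 99.3 | 77.3 / 52.0 |
| Random slope, noise SD 2 | 99.6 / 97.3 | 66.4 / 40.7 |
| Random walk | 99.4 / 96.8 | 66.6 / 40.9 |
| AR(1), rho 0.9 | 100 / 99.9 | 78.5 / 52.7 |
| AR(1), rho 0.8 | 98.7 / 93.2 | 56.1 / 30.8 |
| AR(1), rho 0.65 | 92.1 / 74.9 | 41.3 / 17.5 |
| AR(1), rho 0.5 | 86.1 / 66.1 | 39.2 / 17.5 |

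At a true loss of zero the Wald form rejects in 11.8-14.4% and the score form in 3.0-4.7%. The Wald figures therefore carry some small-sample inflation; the score figures do not, and they show the same order. In the same simulated trials the one-sample t test finds loss below 7.39% in about 2-3% (no benefit), 82-84% (target) and 100% (zero loss).

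A second simulation, with the SD also growing linearly to the last week and AR(1) correlation from 0.3 to 0.95 (Wald test, 400 runs per setting), gave 99-100% with no benefit and 69-75% at the target.

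**The case against.** The strongest reply is that the comparison is already pre-specified in section 10.2: endpoint, window, arm, reference value, test and alpha are all there, so this is a missing cross-reference. In addition, section 2.1 words the objective as estimation, section 10.4.4 will produce a least-squares mean near the end of RT that can be set beside 7.39%, and nothing in 10.4.4 calls the across-time p-value a success criterion. The simulated rates also depend heavily on assumptions.

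Part of this stands. The intended test can be inferred, an end-of-RT estimate will exist, harm requires someone to take the across-time p-value as the primary result, and only the direction of the simulations should be relied on.

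It does not remove the problem. Section 10.2 uses the t test only to justify a number of patients, while the analysis section names a different model for the same endpoint. Where the authors intend no formal test they say so: for 24-month recurrence in 10.4.4 and for Arm 2 in 1.9. Weight loss has no such disclaimer. Recurrence, a secondary endpoint, even has a confidence-interval rule against 20%, while the primary endpoint has none.

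Nor is the planned least-squares mean clearly the sized quantity. Section 10.4.4 measures change from an unspecified baseline, although weight is recorded both before surgery (5.1) and on Day 1 (14.1). It refers to weights within each arm without restricting the primary model to Arm 1, and it does not name the last day of RT.

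A separate caution concerns the 81.8%, which assumes 20 evaluable patients. The June 2020 extension in 10.2 brings Arm 1 to at most 13 + 7 = 20 enrolled. With 15% drop-out about 17 would be evaluable, giving 74.4% power. That is an accrual question and does not bear on which test is primary.

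**Conclusion.** The concern holds and should be corrected before analysis. The trial's one powered hypothesis has no specified test in the section that defines its analysis. The p-value given there answers another question, lacks the stated 80% power, and under every trajectory and covariance tried is significant more often with no benefit (about 66-100%) than at the target (about 18-79%). Those percentages rest on an assumed linear four-week trajectory and assumed covariances and are illustrative. The conclusion itself rests on comparing sections 1.9, 2.1 and 10.2 with 10.4.4. The sample-size calculation is correct.

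**What to change.** In section 10.4.4, state that the primary analysis is a two-sided 5% one-sample t test, with 95% CI, of Arm 1 percent weight loss from the Day 1 weight to the weight on the last day of RT, against 7.39%. Label the weekly GEE profile and its across-time p-value as supportive or descriptive.

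A GEE contrast of the Arm 1 end-of-RT mean with 7.39%, using a small-sample correction, would also address the hypothesis. The t test is the simpler choice because it is the one the trial was sized on. Whichever is used should be fixed before the data are analysed.

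The cost is an amendment to the analysis wording. It needs no new data and no further patients: 20 evaluable patients give 81.8% power, and with SD 5.46 an observed mean below about 4.83% would reject 7.39%.

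### With 13 to 20 Arm 1 patients, Section 10.4.4 relies on GEE sandwich standard errors and names no small-sample correction, test form or reference distribution

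*Combined protocol and SAP*

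**What the plan says.** Section 10.2 defines the endpoint: "The primary endpoint is percent weight loss from Day 1 of treatment to last day of RT". It gives the historical "mean and standard deviation of percent weight loss during POACRT in patients with HPV-related OPSCC are 7.39% and 5.46%, respectively", hypothesises 3.7% for Arm 1, and states that a sample of 20 "will have 80% power to detect the percent weight loss difference if assuming the standard deviation of 5.46% using a two-sided one-group t test". Allowing for drop-out, 24 were to be enrolled in Arm 1.

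The same section reports that in December 2019 "Arm 1 had enrolled only 13 of the target of 20 patients at that time". Accrual was then extended until either 7 more patients joined Arm 1 or 20 more joined in total, so Arm 1 ends with between 13 and 20 patients before any drop-out.

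Section 10.4.4 analyses the weekly percentages with a GEE: identity link, first-order autoregressive working correlation, baseline weight and time points. It plans one p-value for differences across all time points. For the least-square means and mean differences, "their standard errors will be calculated within the use of GEE sandwich method". Analyses are run "at the two-sided 5% significance level". The section does not mention the one-group t test.

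**The concern.** The sandwich estimator is justified for a large number of independent clusters, here patients. With few patients it is biased downward, because it is built from residuals that the fitted model has already shrunk. Using a normal or chi-square reference adds to the problem by treating the estimated variance as known. The t test that sized the trial allows for small samples. The model named for the analysis does so only if a correction and a reference distribution are added, and none is stated.

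The quantity at stake is the end-of-radiotherapy mean. If its interval or standard error is used for the comparison with 7.39%, precision is overstated. If the time-point p-value is reported, its error rate depends on a choice that the plan leaves open.

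**Working it through.** **1. The plan's own figure.** Difference 7.39 − 3.7 = 3.69; SD 5.46; two-sided 5%. Exact one-sample t power (noncentral t) is 79.6% at n = 19 and 81.8% at n = 20, so 20 is the smallest n reaching 80%. Drop-out: 20/0.85 = 23.5, rounded up to 24. Both figures reproduce.

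**2. Hand approximation.** At mean baseline weight, the uncorrected sandwich variance of a weekly mean is Σr²/n², where r are that week's residuals. If the intercept and the baseline-weight slope use up two degrees of freedom, the standard error is too small by a factor of about √((n−2)/n):
- n = 20: √(18/20) = 0.949. Coverage of ±1.96 SE is P(|t₁₈| < 1.96 × 0.949 = 1.859) = 92.1%.
- n = 13: √(11/13) = 0.920. Coverage is P(|t₁₁| < 1.96 × 0.920 = 1.803) = 90.1%.

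**3. Simulation of the stated model.** There were 2,500 trials per setting (Monte Carlo SE √(0.05 × 0.95/2500) = 0.4 points), with complete normal data and SD 5.46. Time was categorical, baseline weight was in the model, and the working correlation was AR(1). The true correlation was AR(1) 0.8, exchangeable 0.5 or a random walk. The number of weekly weights is not stated. Section 5.5 gives Arm 1 radiotherapy over 4 weeks, so four or five post-baseline weights were assumed. Ranges run over these settings:

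| | n = 13 | n = 20 |
|---|---|---|
| Uncorrected SE / true SE, last week | 0.90–0.94 | 0.93–0.98 |
| Coverage, last-week mean, normal 95% interval | 90.0–91.6% | 91.7–93.5% |
| Coverage, first-to-last-week difference | 91.4–92.6% | 92.1–93.2% |
| Time-point test, Wald chi-square, 4 weeks | 16.5–18.4% | 12.5–13.1% |
| Time-point test, Wald chi-square, 5 weeks | 24.0–25.9% | 16.2–17.2% |
| Time-point test, generalised score | 0.9–2.4% | 2.9–3.4% |
| Mancl-DeRouen variance, chi-square reference | 13.0–19.8% | 9.8–13.7% |
| Mancl-DeRouen variance, F reference | 2.6–4.0% | 3.8–4.4% |
| Coverage, last-week mean, Mancl-DeRouen with t | 96.0–96.9% | 95.8–97.0% |

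The coverage rows agree with the hand approximation. With only three weekly weights (AR(1) 0.8), the Wald test rejects 12.2% at n = 13 and 9.4% at n = 20, with coverage of 90.1% and 91.6%. If 20 are enrolled and 15% drop out (20 × 0.85 = 17), coverage with four or five weights is 91.3–91.4% and Wald size 14.7–17.8% (AR(1) 0.8 only). A second simulation (4,000 trials, linear weight loss) gave coverage of 92.0–92.7% at n = 20 and 90.3–92.0% at n = 13.

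**4. Consequence for the 7.39% comparison at n = 20.** The true SE is 5.46/√20 = 1.22. A t test on 19 degrees of freedom needs an observed reduction of 2.093 × 1.22 = 2.56 points. A normal test using the average uncorrected SE needs between 1.96 × 0.928 × 1.22 = 2.22 and 1.96 × 0.978 × 1.22 = 2.34 points. The two would disagree for observed reductions between those limits and 2.56. At the hypothesised 3.69 the ratio is 3.69/1.22 = 3.0, and they agree.

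**The case against.** Several counter-arguments stand in part.

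- **The absence of a correction is read from silence.** Naming the sandwich method does not exclude a corrected version. This stands, so the figures describe the method as normally applied without additions. A plan that intends a correction should say so.
- **A reader might infer that the primary test rejects far more often than 5%.** The document does not support that. Section 10.4.4 does not say whether the time-point p-value is Wald or score, and its sandwich sentence covers the means and differences, not explicitly the p-value. A score test errs in the opposite, conservative direction. Nor does this test compare Arm 1 with 7.39%, so over-rejection cannot by itself produce a false claim of reduced toxicity.
- **No interval for weight loss is specified.** This is correct: Section 10.4.4 promises standard errors and names 95% intervals only for binomial proportions. The coverage figures show what happens if the usual normal interval is built from those standard errors.
- **Thirteen is a floor.** At the observed share, 20 more patients would add 20 × 13/40 = 6.5 to Arm 1, giving about 19 or 20. The n = 20 column is the likelier case before drop-out.
- **The one-group t test may be the primary test.** If so, the comparison with 7.39% already allows for small n. But Section 10.2 names that test only for sizing, and Section 10.4.4 names only the GEE.

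A reader might also extend the point to quality of life, for which Section 10.4.4 reuses the GEE. That analysis covers all arms on a different visit schedule and was not computed, so no size is claimed for it.

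**Conclusion.** The concern holds as a moderate defect in the inference for the primary endpoint. Applied without additions, the named method gives a last-week standard error about 2% to 10% too small on average, and a normal-based 95% interval that covers about 90% to 93.5%. The error rate of the time-point test is undetermined: about 12% to 26% if Wald chi-square, about 1% to 3.5% if generalised score. Neither holds 5%.

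These sizes rest on 13 to 20 patients, four or five weekly weights, complete normal data and the three correlation patterns used; missing weights were not simulated. They do not show that the primary conclusion would be wrong. At the hypothesised effect the answer is unchanged, and the difference matters only for a result near the significance boundary.

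**What to change.** In Section 10.4.4, specify one of the following:
- a bias-corrected sandwich such as Mancl-DeRouen, together with a t/F reference whose degrees of freedom are based on the number of patients; both parts are needed, because the corrected variance with chi-square still rejects 9.8% to 19.8%;
- a mixed model for repeated measures with Kenward-Roger degrees of freedom, a standard alternative that was not simulated here.

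State the form of the time-point test. State also that the Arm 1 comparison with 7.39% uses either the last-day-of-radiotherapy estimate from the chosen model or the one-group t test from Section 10.2.

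The cost is a short SAP addition and slightly wider intervals. In the simulation the first option was mildly conservative: coverage 95.8% to 97.0% and test size 2.6% to 4.4% over n = 13 and 20, apart from a few settings at n = 13 where coverage was 96.0% to 96.9%, inside the same range.

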2.2 Secondary Objectives

1. To evaluate the narcotics administration of patients 6 weeks after POAmCRT (Arm 1).
2. To determine the disease recurrence rate at 24 months post-treatment in each arm.

3. To determine progression free survival (PFS) and overall survival (OS) for each arm.
4. To evaluate the proportion of PEG tube placements in each arm.
5. To determine the serum creatinine changes in patients receiving POAmCRT (Arm 1).

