4.0 REGISTRATION PROCEDURES

Patients must not start any protocol intervention prior to registration through the Siteman Cancer Center.

The following steps must be taken before registering patients to this study:

1. Confirmation of patient eligibility
2. Registration of patient in the Siteman Cancer Center OnCore database
3. Assignment of unique patient number (UPN)

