5.3 Interim Assessment

The interim assessment will include the following tests or procedures and should occur within 14-42 days of surgery:

1. Clinical examination.
2. Documentation of key data from the pathology report: T (1-4) and N (0-3) stage, ECE status (+/-) and extent of ECE (mm), margin status (+/-).
3. Arm assignment (based on pathology data)
4. Documentation of patient symptoms using NCI-CTCAE version 4.0; please note that AEs considered at least possibly related to surgery need not be recorded.
5. Documentation of ECOG performance status.
6. Completion of QOL questionnaires.
7. Documentation of Comorbidity Index.
8. Laboratory evaluations: CBC, BMP, magnesium, PT/PTT.
9. OPTIONAL: Speech and swallowing assessment including MBS and PSS-HN questionnaire.

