5.7 Evaluations for Toxicity and Disease Relapse

All patients who receive any study treatment (starting point of “study treatment” is first dose of post-operative RT) are evaluable for toxicity. Patients are evaluated from first day of study treatment until five years after the conclusion of treatment, or death.

All patients who undergo surgery are evaluable for disease relapse.

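### Section 10.4.4 sets the PEG proportion over all enrolled patients with no arm split, in conflict with the per-arm objective in 2.2 and the RT-started toxicity set in 5.7

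*Combined protocol and SAP*

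**What the plan says.** Section 2.2, objective 4: "To evaluate the proportion of PEG tube placements in each arm".

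Section 10.4.4 names the endpoint and its population together: "The secondary endpoints include proportion of PEG tube placements for all enrolled patients". The sentence on estimation repeats that population, "Proportions of PEG tube placements for all enrolled patients", and attaches a binomial 95% interval. Neither sentence mentions arms. Elsewhere in 10.4.4, creatinine and narcotics are tied to POAmCRT (the Arm 1 regimen), while recurrence and adverse events are given by arm.

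Section 1.9 classes PEG as toxicity: "Secondary endpoints of mucosal toxicity to be determined include the proportion of patients who had PEG tubes placed". It is also a component of the composite that is hypothesised to fall from 72.6% to 36.3% after POAmCRT.

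Section 5.7 defines the toxicity set as patients who received any study treatment, whose starting point "is first dose of post-operative RT) are evaluable for toxicity". It defines a separate, surgery-based set for relapse.

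Section 4.0 places registration first: "Patients must not start any protocol intervention prior to registration". The arm is fixed at the interim assessment, 14 to 42 days after surgery (Section 5.3): "Arm assignment (based on pathology data".

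**The concern.** The objective and the analysis describe different quantities. There are two separate conflicts.

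- **Arm.** The objective is per arm; the analysis names one population covering 42 Gy with one cisplatin dose, 42 Gy alone, and 60 Gy with or without three cisplatin cycles. A single proportion over these patients describes none of the regimens.
- **Denominator.** PEG is a toxicity endpoint, so Section 5.7 points to patients who started RT. Enrolment precedes surgery and arm assignment follows it, so the enrolled set can contain patients with no RT and even no arm.

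At stake is whether the reported PEG figure can be read as evidence on the toxicity of the de-intensified regimen, which is the purpose given in Section 1.9. Under the literal rule it also reflects the arm mix and the number of patients who leave before RT.

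**Working it through.** **1. No plan figure exists for PEG.** The documents give no PEG target, power or sample size. The only powered figure concerns weight loss: with a difference of 7.39 − 3.7 = 3.69, SD 5.46 and a two-sided one-sample t test at 5%, power is 81.8% at n = 20 (79.5% at n = 19). Then 20/0.85 = 23.5, rounded up to 24. This reproduces the plan but does not bear on PEG.

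**2. Share of the enrolled set outside Arm 1.** Inputs are from Sections 10.1 and 10.2.

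| Situation | Not in Arm 1 |
|---|---|
| Mix expected in 10.1 (90/5/5) | 10% |
| December 2019: 13 of 40 in Arm 1 | 27/40 = 67.5% |
| Extension, next 7 patients all in Arm 1 | 27/47 = 57.4% |
| Extension, 20 more patients, 7 of them in Arm 1 | 40/60 = 66.7% |
| Extension, 20 more patients, none in Arm 1 | 47/60 = 78.3% |

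The documents do not divide the 27 between Arm 2, Arm 3 and no arm.

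**3. Effect of one figure across arms.** Let w₁, w₂, w₃ be the arm shares and p₁, p₂, p₃ the PEG proportions, ignoring patients without an arm. The all-arm figure minus the Arm 1 figure is

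w₂(p₂ − p₁) + w₃(p₃ − p₁).

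Its absolute value is at most (w₂ + w₃) times the larger of |p₂ − p₁| and |p₃ − p₁|. The multiplier is 0.10 at the mix in 10.1, 0.675 at the December 2019 count, and 0.57 to 0.78 after the extension. The two terms can have opposite signs: Arm 2 drops cisplatin, while Arm 3 receives 60 Gy. No p is given, so neither sign nor size follows.

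**4. Effect of the denominator.** Let f be the fraction of enrolled patients who never start RT, q the PEG proportion recorded among them, and p the proportion among those who start. The all-enrolled figure is (1 − f)p + fq, which differs from p by f(q − p). The documents give neither f nor q. Section 10.4.4 counts placements without excluding tubes placed around surgery, so q need not be zero. The PEG form is first due 6 weeks after completion of adjuvant therapy (Sections 11.0 and 14.2). A patient who never starts RT has no such date, and the plan does not say how that patient is scored.

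**5. Precision.** With assumed counts, used only to show interval width, exact (Clopper-Pearson) 95% intervals are:

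| Set | Assumed count | Proportion | 95% interval |
|---|---|---|---|
| Arm 1 | 4/20 | 20% | 5.7% to 43.7% |
| Arm 2 | 1/14 | 7.1% | 0.2% to 33.9% |
| Arm 3 | 3/6 | 50% | 11.8% to 88.2% |
| All | 8/40 | 20% | 9.1% to 35.6% |

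The combined interval is narrower but describes a mixture.

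**The case against.** The strongest reply is that combining the arms is inferred. Section 10.4.4 never says the figure is overall. Section 2.2 limits narcotics and creatinine to Arm 1 but not PEG, and 10.4.4 follows the same pattern, so the wording may mean every arm rather than Arm 1 only. Baseline tables are by total and by arm, and toxicity is collected by arm. This reading is possible. It would remove the arm conflict but leave the denominator conflict with Section 5.7, and a sentence with two readings that give different numbers still needs settling.

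The stakes are also limited. PEG alone is a descriptive secondary endpoint with no threshold or test. Arm is known for every treated patient, so per-arm counts can be produced whatever 10.4.4 says. That stands, and it makes the correction cheap.

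The December 2019 share is an interim snapshot, which is why a range for the final share is shown.

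**Conclusion.** The conflict holds. Followed literally, 10.4.4 does not deliver objective 4 of Section 2.2, and it uses a wider denominator than Section 5.7 allows for toxicity. The documented size is the share of the enrolled set outside Arm 1: 67.5% in December 2019, and about 57% to 78% under the extension. The arm half rests on the literal reading; the denominator half does not depend on it. The matter should be corrected, but it does not touch the primary endpoint or its sample size.

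Three stronger inferences are not supported:

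- **That the figure understates PEG use in Arm 1.** A reader might apply the 6% and 41% rates in Section 1.4 to the arms. Those rates compare no primary-bed radiation with primary-bed radiation, and under Section 5.5 Arm 2 receives 42 Gy to the tumor bed just as Arm 1 does. They are not arm rates.
- **That patients who leave before RT can only lower it.** This requires that they have no tube and are scored as such; the plan establishes neither.
- **That the planned 15% drop-out measures the dilution.** It is the Arm 1 allowance for the weight-loss endpoint, not a rate of failing to start RT.

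**What to change.** In Section 10.4.4, in both sentences that set the PEG population, replace the all-enrolled wording with: *in each arm, among patients who received at least one dose of post-operative RT (Section 5.7), with a 95% CI per arm*. List patients who left before RT separately, with the reason. Give any all-enrolled figure as supplementary only. It would help to state whether a tube already in place at the first RT dose counts, since restricting the set does not settle that.

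The cost is a wording change with no new data. The per-arm intervals are wider than a combined one, especially in Arm 3 with about 6 patients. That width reflects the information available on each regimen.
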